9.0 Multi-Institutional Guidelines: N/A	
10.0 Pharmaceutical and/or Investigational Device Information	
11.0 Reference:	
Appendices:	

Précis

The overall aim of this proposal is to compare the effectiveness of an image guided approach to lipid lowering to standard therapy guided by clinical risk factors and blood lipid levels. Men and women over age 55 who are candidates for statin therapy will be randomized to usual cholesterol lowering care, or to care guided by MRI images of the carotid arteries. Participants randomized to the second, imaging guided, group will be assigned to LDL cholesterol targets according to the degree of atherosclerosis seen by MRI. The study endpoints will be the total degree of plaque regression seen, the dosage of statin drugs required to achieve that reduction, and the rate of cardiovascular events.

FDG-PET is hypothesized to enable visualization of anti-inflammatory effects of statins that most likely occur before anatomic regression of the plaques can be demonstrated on MRI.¹ A pilot substudy is to be conducted to explore this relationship. A subgroup of patients participating in the main study will be asked to participate in FDG PET imaging. The purpose of this pilot study is to determine if FDG avid lesions undergo a greater degree of morphologic regression with therapy controlling for the reduction in LDL cholesterol and the dosage of statins required to achieve that target.

Although contrast-enhanced coronary CT angiography (CTA) with multidetector computed tomography (MDCT) has been used extensively to characterize coronary artery plaque composition, there is little data regarding its reproducibility. A recent study demonstrated excellent reproducibility for this technique but this study was performed using the older 64 detector row CT scanners². A pilot substudy will be conducted to study the reproducibility of coronary CT angiography using the newer generation of 320 detector row CT scanners.

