It is widely postulated in the literature that ¹⁸F-fluorodeoxyglucose (FDG) imaging can improve risk assessment and prognostication through the identification of high-risk "vulnerable" plaques, plaques that demonstrate heightened inflammation, neovascularization or apoptosis. The primary target is the carotid and coronary arteries, imaging will also include the ascending and descending aorta, and the iliac arteries. Successful FDG PET imaging has been performed in large vascular beds, including the carotid arteries, and recent preliminary reports suggest the potential for noninvasive coronary plaque imaging. The advantage of nuclear imaging is that multiple vascular beds can be imaged with a single radionuclear isotope administration.

In a subset of 60 individuals we plan to study the reproducibility of arterial stenosis and plaque volume as measured by MDCTA.

At present, there is no available data on the reproducibility of 320 detector row MDCT for measuring arterial stenosis and plaque volume. This data will allow investigators to determine whether measured changes in stenoses and plaque morphology exceed that expected from the limits of measurement error in CTA and thus make the results of ongoing trials more reliable.

Consistent with such objectives, our specific aims are:

1st Aim

To examine whether image guided lipid lowering therapy is superior to NCEP guided therapy in promoting carotid atherosclerotic plaque regression and stabilization.

2rd Aim

To investigate whether the observed change in carotid atherosclerosis volume measured by MR, parallels observed change in coronary atherosclerosis volume measured by MDCT angiography.

3rd Aim

To examine whether MRI guided plaque regression and stabilization produces greater reduction in clinical CV events than standard NCEP guided therapy.

4th Aim

To examine the statin dosages required to promote plaque regression and stabilization differ between conventional and image guided strategies.

5th Aim

To investigate whether FDG PET activity predicts carotid morphological plaque regression and stabilization in both the carotid and coronary arteries and compare the efficacy of PET based prediction with MRI.

6th Aim

To correlate FDG uptake in the carotid, coronary, aortic, and iliac arteries with absolute values and changes in hematological biomarkers of vascular inflammation, thrombosis and atheroprotection at and between each time point.

7th Aim

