A subgroup of 60 patients will be recruited to participate in PET scanning which will be performed twice, once at study initiation and after 6 months of trial-directed statin therapy.

Information including cardiovascular risk factors and other medication, including anti-inflammatory drugs, use will be collected. The total cholesterol and LDL levels and the dosage of statins required to achieve that target will be recorded.

Inclusion Criteria:

Participants who are not participating in the CT Reproducibility study are eligible.

Exclusion Criteria:

Patients who are unable or unwilling to comply with the physical activity restrictions or fast for 12 hours prior to FDG PET scanning will be excluded. Due to the need for dietary manipulation and the maintenance of strict glycemic control we will exclude diabetic patients from our initial study sample. Blood glucose measurements before injection must be within normal limits, less than 200 mg/dL (11 mmol/L).

Hematological Biomarkers Markers:

Blood tests for inflammatory markers will be incorporated into the baseline and 6 month blood draws. Standard investigations will include C-reactive protein, matrix metalloproteinase -3 and -9, interleukin-18, cathepsin K, fibrinogen, adiponectin, and plasminogen activator.¹²⁻¹³ A tube of blood will be stored at -70°C for testing of further markers defined at a later date.

FDG PET Preparation:

Study subjects will be asked to fast for 12 hours prior to PET scan. On the morning of the PET study, a low carbohydrate meal will be provided to study participants. Patients will be asked to avoid exercise 24 hours prior to scanning.

Carotid and Cardiac FDG PET Imaging Technique: On the morning of the scan, Metoprolol 50 - 100 mg PO will be administered to slow the heart rate and optimize the acquisition of diastole.¹

The dose of FDG administered, duration between FDG injection and PET image acquisition, and the method of quantification of FDG uptake will be standardized.¹⁵ The injected dose of 18F-fluorodeoxyglucose will be 5.2 MBq/kg (140 mCi/kg) of lean body mass to a maximum of 12.5 mCi.

Patients will be kept resting comfortably in a semi-dark room. Scanning will be initiated after 90 minutes.¹⁶⁻²⁰ Typically, extended time imaging will be performed of the coronary and carotid beds first, followed by a 5 - 15 minute break and imaging of the remainder of the body.

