In order to facilitate the comparison between MRI and PET imaging prior to the availability of the integrated MR/PET unit, an additional high resolution carotid MRA examination will be performed at the 6 month time point. This gadolinium enhanced study will use the standard carotid MRA study protocol and be scheduled on the same day or within a 2 week interval from the PET scan. Carotid positioning will be reproduced through positioning technique using careful measurement, such as the distance between the chin and sternal notch, and employing mobility-restricting equipment, like the head holder and tape reminders.

Image Reconstruction and Registration of Carotid and Cardiac FDG PET Imaging:

PET image reconstruction will use standard filters for a fully iterative process using optimized spectral content measure with at least 2 iterations and 28 subsets. High resolution reconstruction of the neck will be performed using at least 256 x 256 matrices; other vascular beds will be reconstructed using at minimum the standard 128 x 128 matrices.

Matching PET/CT and MR/PET images will be fused.¹¹ Both vendor specific software and open source programs will be used for region of interest delineation for partial volume correction and for vessel wall and lumen for calculation of vessel wall FDG uptake.²²

Imaging of the thorax will be viewed as both summed and gated reconstructions. For the gated reconstruction, 8-frames per cardiac cycle will be binned and the usable frames from middle to late diastole that have minimal blurring will be extracted and summed to enhance count density of the coronary arteries and warped for co-registration with the diastolic and respiratory gated CT / MR data.

Data Analyses of FDG PET Imaging:

For each patient scan, quantitative analysis will be performed of carotid and coronary arteries, aortic arch, ascending and descending aorta, abdominal aorta and iliac vascular territories. Arterial wall lesions with radioactivity concentrations above the mean blood-pool activity, and/or with calcification detected by CT and with morphology consistent with that of a plaque will be considered plaque and included in the assessment. CT / MR evaluation will be performed to identify atherosclerotic plaque as abnormal wall thickening with or without the presence of other features, like a lipid core or focal calcification, on a segment by segment basis. Maximum standardized uptake value (SUV_{max}) corrects for patient weight and injected dose-decay:

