Using appropriate parametric and non-parametric tests at and between both the baseline and 6 month time points, a comparison of the presence or absence of atherosclerotic plaque by PET and CT / MRI will be performed. FDG accumulation (with both TBR and SUV_{max}) will be compared across different plaque morphology and compositions defined by MR / CT (for example, presence of a lipid core or calcification). Correlation between imaging findings and changes will be made with age, gender, traditional risk factors (height, weight, hypertension, etc.), absolute values and changes in statin dose, total cholesterol, LDL, HDL, triglycerides and hematological biomarkers markers of inflammation, thrombosis and atheroprotection.

For Hypothesis 8:

Agreement between the two blinded readers of semiquantitative measures of CT angiographic stenosis will be measured using weighted kappa. Quantitative analyses of coronary arterial wall volume, lumen volume and plaque composition will be assessed using the intraclass correlation coefficient (ICC) and Bland-Altman plots.

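### The analysis planned for Hypotheses 5 to 7 does not answer the PET substudy's stated question: no model relates FDG uptake to later plaque regression with adjustment for LDL reduction and statin dose

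*Combined protocol and SAP*

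**What the plan says.** The Précis gives the purpose of the PET pilot: to learn whether "FDG avid lesions undergo a greater degree of morphologic regression with therapy controlling for the reduction in LDL cholesterol and the dosage of statins" needed to reach the target. Aim 5 in section 1.2 is "To investigate whether FDG PET activity predicts carotid morphological plaque regression and stabilization in both the carotid and coronary arteries", and it adds a second task, to "compare the efficacy of PET based prediction with MRI". FDG uptake in the carotid and coronary arteries is secondary endpoint D in section 1.1.

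On the design, section 1.3 plans two PET scans in each of 60 participants, timed "once at study initiation and after 6 months of trial-directed statin therapy".

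The analysis text for Hypotheses 5, 6 and 7 in section 6.0 is one short paragraph. It opens "Using appropriate parametric and non-parametric tests", is limited to the baseline and 6-month visits and the interval between them, and contains three items:

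- plaque presence by PET against CT/MRI;
- FDG accumulation (TBR and SUVmax) across plaque types defined by MR/CT;
- correlation of imaging findings and changes with age, sex, risk factors, statin dose, lipids and blood biomarkers.

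The linear mixed models in the same section are assigned to Hypotheses 1, 2 and 4. Their stated terms are time and treatment.

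**The concern.** A prediction question needs an outcome (regression), a predictor measured earlier (FDG uptake) and, here, two named adjustment variables. None of the three listed items has that form. LDL and statin dose appear as things to correlate with, not as covariates in a model of regression. The visits named stop at 6 months, whereas regression is imaged later.

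Section 1.3 also measures uptake by region of interest, segment and vascular territory, so each patient supplies several values. Section 6.0 does not say whether the patient, vessel or lesion is the unit of analysis.

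At stake is whether 60 patients' paired PET scans, and the added 6-month contrast MR, yield an answer to the question that justified them. An analyst would also be free to choose the model, covariates and unit after seeing the data.

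**Working it through.** **1. Question against analysis**

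| Element of the question (Précis, Aim 5) | In the section 6.0 text for Hypotheses 5 to 7? |
|---|---|
| Regression as outcome, FDG uptake as predictor | No such test named |
| Control for LDL reduction and statin dose | Listed only as correlates |
| Carotid and coronary regression | Only baseline and 6 months covered |
| PET prediction compared with MRI prediction | Absent |
| Unit of analysis with several regions per patient | Not stated |

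The correlations with blood biomarkers do serve Aim 6. The gap is in Aim 5 and the Précis purpose.

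**2. When the images exist** (section 1.3, Appendix B)

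| Image | Baseline | 6 months | 12 months | 24 months |
|---|---|---|---|---|
| FDG PET (substudy) | yes | yes | no | no |
| Carotid MR | yes | PET participants only | yes | yes |
| Coronary CT angiography | yes | no | no | yes |

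An analysis confined to baseline and 6 months could at most see early carotid change. It has no scheduled coronary CT angiography outcome. The Précis itself expects the anti-inflammatory effect to precede regression visible on MRI, so the 12- and 24-month images are the relevant ones.

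**3. What the substudy can detect**

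The documents give no power or precision figure for the PET aims, so there is nothing to reproduce. A patient-level approximation, two-sided 5%, 80% power, n patients and k covariates:

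r = tanh[(1.96 + 0.84) / √(n − k − 3)]

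- n = 60, k = 2 (LDL change, statin dose): 2.80/√55 = 0.378, r = 0.36.
- n = 48, k = 2: 2.80/√43 = 0.427, r = 0.40. Here 48 = 60 × 0.80, using the main study's 20% attrition as an assumption for this subset.
- Adding baseline volume and arm (k = 4): 2.80/√53 = 0.385, r = 0.37; 2.80/√41 = 0.437, r = 0.41.

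**4. Why adjustment matters (illustrative)**

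In 4,000 simulated data sets, uptake and regression each correlate with LDL change but have no direct link. With 60 patients and correlations of 0.3, an unadjusted test rejects 11% of the time; with 0.5, 50%. The adjusted test stays near 5%. These correlations are assumed.

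**5. Why the unit matters (illustrative)**

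Suppose a lesion-level correlation were run as if lesions were independent, with m lesions per patient and the same within-patient correlation ρ in both measures. The variance is inflated by about 1 + (m − 1)ρ². Simulated type I error at nominal 5%, 60 patients, 4,000 runs each:

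| m | ρ | Inflation | Type I error |
|---|---|---|---|
| 2 | 0.4 | 1 + 1 × 0.16 = 1.16 | 0.06 |
| 4 | 0.4 | 1 + 3 × 0.16 = 1.48 | 0.10 |
| 4 | 0.6 | 1 + 3 × 0.36 = 2.08 | 0.17 |
| 8 | 0.6 | 1 + 7 × 0.36 = 3.52 | 0.31 |

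For a patient-level correlate such as LDL, the inflation is 1 + (m − 1)ρ. At m = 4 and ρ = 0.4 it is 2.2, so 240 lesions count as about 109 and the type I error is about 0.19. The documents give neither lesion counts nor within-patient correlations; all are assumed.

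**The case against.** The strongest reply is that this is a pilot in 60 patients meant to explore a relationship, that FDG uptake is one of five secondary endpoints, and that brief analysis text is normal at that level. The changes between baseline and 6 months could also include early carotid change, since PET participants have a 6-month carotid MR. The pilot status stands as a limit on how serious the point is. It does not supply the missing analysis: no test of uptake against regression is named even over those 6 months, and the coronary half of Aim 5 cannot be reached there by CT angiography.

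Two stronger readings are tempting and are not supported.

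- A reader might infer that the plan treats lesions as independent, so its p-values will be too small. Section 6.0 names no method and no unit, so clustering is neither handled nor excluded. The type I error figures show a risk if a naive test were run, not a property of the plan.
- A reader might infer that agreement between PET and CT/MR is inflated by a shared criterion, because section 1.3 admits "Arterial wall lesions with radioactivity concentrations above the mean blood-pool activity, and/or with calcification detected by CT". That sentence goes on to require morphology consistent with plaque and reads as a rule for which lesions enter the assessment. The next sentence defines CT/MR plaque separately, by abnormal wall thickening with calcification optional, and the TBR text distinguishes FDG-avid plaque from FDG-negative areas with plaque features. Inflation is not shown.

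**Conclusion.** The point holds as a mismatch between purpose and analysis. The plan for Hypotheses 5 to 7 contains no model of later regression on FDG uptake, no adjustment for LDL reduction and statin dose, and no comparison of PET with MRI as predictor. The unit of analysis is unspecified. This rests on the text alone and needs no numerical assumption.

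Its reach is limited to Aim 5 and the PET substudy; the primary endpoint is untouched. Even with the right model the substudy is imprecise: partial correlations below about 0.36 (60 patients) or 0.40 (48 patients, assumed loss) would probably be missed. The simulated error rates in the last two steps of the working depend wholly on assumed correlations and lesion counts and are illustrative only.

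**What to change.** In the section 6.0 text for Hypotheses 5 to 7, specify for Aim 5:

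- **Carotid:** change in wall volume at 12 and 24 months, modelled on baseline TBR and adjusted for baseline volume, LDL change, statin dose and arm, with a patient random effect. Use the vessel as the unit, because section 1.3 sums slice areas by vessel. Use the lesion only where lesions can be matched across scans.
- **Coronary:** change in plaque volume from baseline to the 24-month CT angiogram, modelled in the same way. There is no 12-month coronary image.
- **PET against MRI:** compare the predictive value of baseline TBR with that of baseline MRI plaque features for the same outcomes.
- **Clustering:** a patient random effect or patient-clustered errors wherever more than one vessel, segment or region per patient is analysed.
- **Reporting:** estimates with intervals, labelled as pilot results.

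Section 7.4 records that the study moved to data analysis only in January 2017. The text should therefore be dated before PET and regression data are linked; if they already have been, the analysis should be labelled post hoc.

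The cost is plan wording and some added analysis work, using images already scheduled. A lesion-level version would also need lesion matching that the documents do not describe. The downside is wider intervals in about 60 patients.

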7.0 Human Subject Protection

7.1 Rationale for Subject Selection

Individuals over age 55 from all racial/ethnical groups are eligible to participate. NIH employees over age 55 who meet the eligibility requirements are eligible to be screened and considered for protocol participation.

Recruitment and enrollment of NIH employee subjects will be consistent with NIH HRPP SOP 14 F Section 3.1. We intend to allow enrollment of staff who are affiliated or subordinate to the Principal Investigator, including technologists, nurses, scientists, students and family members. We believe we can offer them the opportunity to participate without coercion. Consent for such subjects will not be obtained from individuals in their supervisory chain of command. Refer to the NIH Policy Manual, 2300-630-3 - Leave policy for NIH Employees Participating in NIH Medical Research Studies.

This age group is the most likely group to suffer the clinical events consequent to atherosclerosis. Atherosclerosis and concomitant cardiovascular events are the leading cause of death in all major racial/ethnic subgroups in industrialized nations, Efforts to reduce the burden of cardiovascular disease is powerfully relevant to persons of all ethnicities. Our planned enrollment has been selected to be representative of the general gender and ethnic demographic subgroups of the greater Washington DC area (appendix F). The advent of MRI techniques powerful enough to allow for precise guantification of plague growth and regression, as well as alterations of plaque architecture and composition, has made available a number of novel indices of atherosclerotic burden and plaque vulnerability. This study is designed to investigate the comparative effectiveness of image guided lipid therapy with standard NCEP guided therapy with HMG-CoA reductase agents on the progression of carotid and coronary atherosclerosis as sub-clinical markers of cardiovascular atherosclerotic disease.

PET Substudy

A subgroup of 60 patients will be recruited to participate in PET scanning

Reproducibility Substudy

A subgroup of 60 participants who had one RR interval CT scan will be asked to return 4 weeks after their initial scan for a second scan using the same protocol. The inclusion criteria for this substudy -- single heartbeat (one RR interval) scan with <10.5 mSv estimated dosage -are selected to keep radiation exposure as low as can be achieved while assessing the reproducibility limits of this method. Additionally, the protocol indicated and reproducibility scans will cumulatively administer less than the 21 mSv radiation dosage specified in the consent document. Patients will not undergo calcium scanning during the reproducibility scan and they will not be eligible for the PET substudy. Sixteen to twenty-four patients will be selected from three groups: (a) patients with a calcium score of 0-99, (b) patients with a calcium score -100-399 and (c) patients with a calcium score of > 400. These 60 scans will be interpreted by two readers, allowing assessment of both intra and interobserver variability as well as repeatability limits.

A comprehensive strategy of advertising and recruitment through the NIH clinical center patient recruitment and referral center will be

utilized including radio and internet PSAs as well as print flyers. (Appendix G) The Johns Hopkins Clinical Trial Unit database will also be used to identify qualifying participants, pending IRB approval at that institution. This database contains a rich population of patients in preventive cardiology clinics who have identified themselves as interested in participation in clinical trials.

Searches of the electronic medical record, radiology records and patient registries at Suburban hospital will be performed to identify and recruit patients meeting inclusion criteria for this study under a HIPAA waiver granted by the Suburban Privacy Board.

7.2 Participation of Children:

Atherosclerotic disease is not a disease of childhood and will not be eligible for participation in this study, based on the fact they are unlikely to have this disease.

7.3 Evaluation of Benefits and Risks/Discomforts:

Phlebotomy

Associated risks include anemia and hematoma and minor pain at the puncture site.

Beta-Blockers (Atenolol and Metoprolol

Atenolol and metoprolol are FDA approved selective β 1 receptor blocker used in treatment of several diseases of the cardiovascular system, especially hypertension, angina or myocardial infarction. The side-effects include tiredness and dizziness (10%), depression (5%), rash (5%), diarrhea (5%) shortness of breath (3%), chest pain (1%), wheezing (1%). Palpitations, congestive heart failure, peripheral edema, syncope, chest pain, dry mouth, gastric pain, constipation, flatulence, digestive tract disorders, heartburn, hypotension, mental confusion, short-term memory loss, headache, somnolence, nightmares, and insomnia reported in very rare instances (<1%).

Calcium-channel Blockers (Diltiazem)

Diltiazem is a FDA approved cardiovascular medication for the treatment of hypertension, angina or rate control of atrial fibrillation/flutter or conversion of supraventricular tachycardia. The side-effects of chronic use include lower extremity edema (2-15%), headache (5-12%), first degree AV block (2-8%), bradycardia (2-6%),

hypotension (<2%-4%), vasodilation (2-3%), extrasystoles (2%), flushing (1-2%), dizziness (3-10%), nervousness (2%), rash (1-4%), dyspepsia (1-6%), constipation (<2-4%), vomiting (2%), diarrhea (1-2%), weakness (1-4%), myalgia (2%), rhinitis (<2-10%), pharyngitis (2-6%), dyspnea (1-6%), bronchitis (1-4%), cough (<3%) and sinus congestion (1-2%).

StatinTherapy

HMG CoA-Reductase inhibitors (statins) are generally well tolerated. Clinically important adverse effects of the drugs include increases in serum transaminase concentrations and myositis, with and without complicating rhabdomyolysis. ⁽²⁹⁾ Statin monotherapy can result in elevation of liver enzymes, most often \leq 3 times the upper limit of normal. These elevations typically normalize without lasting injury upon discontinuation of the drug. Their clinical significance is uncertain given the extremely rare occurrence of statin related toxic hepatits⁽¹⁶⁾.

In 7 studies to date reporting rates of clinical myositis, elevation of creatinine kinase (CK) > 10 times the upper limit of normal and rhabdomyolysis, the combined incidence of these events has been less than $0.7\%^{(10, 31-35)}$. The highest reported rate of rhabdomyolysis was 0.53%, observed with simvastatin 80 mg daily. ⁽³⁶⁾

The use of high dose, intensive statin therapies to achieve very low LDL levels is a recent development. Available data, including three large randomized controlled trials (the A to Z, TNT and IDEAL studies), indicate that high-dose statins (atorvastatin 80 mg daily, simvastatin 80 mg daily) are associated with low rates of serious musculoskeletal (<0.6%) and hepatic (<1.3%) injury. ^(33, 34, 36, 37)

Ionizing Radiation

Low dose CTA angiography and FDG PET/CT (as used in this protocol) carries a conservatively estimated lifetime additional risk of malignancy less than 0.2% in women and less than 0.1% in men, on a background lifetime risk of approximately 30%.³⁸⁻⁴⁰The primary prevention population targeted for this study is unlikely to receive significant degrees of medical radiation during the 24 months of study follow up.

This study uses statin drugs for the FDA approved indications of treatment of hypercholesterolemia. The study is not designed or intended to test new indications, dosages, routes or study populations for statin drugs. The research question underlying this protocol is strictly limited to the issue of risk stratification approaches, not to how that risk is treated. The use of statins in this study meets the six conditions for IND exemption.

1. it is not intended to be reported to FDA in support of a new indication for use or to support any other significant change in the labeling for the drug;

2. it is not intended to support a significant change in the advertising for the product;

3. it does not involve a route of administration or dosage level, use in a subject population, or other factor that significantly increases the risks (or decreases the acceptability of the risks) associated with the use of the drug product;

4. it is conducted in compliance with the requirements for IRB review and informed consent [21 CFR parts 56 and 50, respectively];

5. it is conducted in compliance with the requirements concerning the promotion and sale of drugs [21CFR 312.7]; and

6. it does not intend to invoke provisions regarding emergency research under 21 CFR 50.24.

Gadolinium enhanced MR

The use of MR contrast containing gadolinium chelates is generally considered to be safe, with an extremely rare incidence of idiopathic allergic reactions. Use in a population with severe (stage 4 to 5) renal dysfunction is the exception to this rule. Patients with severe or end-stage renal impairment and concomitant gadolinium chelate exposure are at risk for development of the fibrosing disorder nephrogenic fibrosing dermopathy (NSF), with 2.5-5% of patients with end-stage renal disease on dialysis developing NSF subsequent to gadodiamide exposure. The FDA currently defines the at-risk population as patients with estimated GFR <30 mL/min/m² or those with any degree of renal dysfunction due to the hepatorenal syndrome or peri-hepatic transplant period.^{41, 42} The FDA has no reports of NSF in patients with mild-to-moderate renal insufficiency (ie, eGFR>29 ml/min/m²) or normal renal function

(http://www.fda.gov/NewsEvents/Newsroom/PressAnnouncements/200 7/ucm108919.htm). To ensure participant safety and provide a wide safety margin, participants with estimated GFR < 45 mL/min/m² will be ineligible for gadolinium chelate contrast administration during this study.⁴³

lodinated contrast

The primary known risks of nonionic iodinated contrast as utilized in MDCT angiography are hypersensitivity reactions and contrast induced nephropathy. Mild to moderate adverse events such as nausea, injection site pain or urticaria occur in less than 3 percent of patients. Serious adverse events, such as hypotensive collapse, shock and death are reported in less than 1 in 10,000 patients. These reactions are generally considered idiosyncratic. Contrast induced nephropathy (CIN) is defined by an increase in creatinine more than 1 mg/dL or 50% above baseline. The risk of CIN in patients with normal renal function is considered to be negligible. The inclusion criteria for this

study require baseline GFR >45 mL/min/m² as calculated by the MDRD equation to minimize risk of nephropathy. Furthermore, injection of less than 100 ccs of iodinated contrast medium is considered to present minimal risk of CIN. The proposed MDCT angiographic protocol utilizes ~60cc of contrast.⁴⁴

F-18 Fluorodeoxyglucose

F-18 fluorodeoxyglucose (FDG) is an analog of glucose with an excellent safety record. In a four year multicenter study of 81,801 FDG administrations, involving one-third of the United States PET facilities, not a single adverse reaction was detected with 95% confidence limits from 0-3.7/100,000.⁴⁴ This finding is consistent with observations made across all radiopharmaceuticals. In a prospective study of over 750,000 administrations in 18 major United States medical centers the prevalence of reactions was 2.3/100,000 with 95% confidence limits of 1.2-3.4/100,000.⁴⁶

